# 4.3. Justification for Dose

The 4-mg QD dose of baricitinib selected for this study in a patient population with COVID-19 infection is based on clinical data showing an effect of baricitinib on inhibition of cytokine signaling. Upregulation of multiple proinflammatory cytokines has been shown in patients with COVID-19 infection admitted to ICU units in Wuhan, China, and elevated IL-6 was a predictor of mortality in COVID-19 patients in another China-based study.

In patients with RA, there was a dose-dependent reduction in plasma IL-6 levels, assessed after 12 weeks of treatment. In ex vivo studies, there was a similar dose-dependent effect on inhibition of multiple cytokines implicated in COVID-19 infection. In a compassionate use program in pediatric patients with chronic atypical neutrophilic dermatosis with lipodystrophy and elevated temperature (CANDLE) syndrome, patients on a mean dose of baricitinib 6-mg QD showed a striking reduction in cytokine signaling (Sanchez et al. 2018). In healthy volunteers, exposures observed at the baricitinib 4-mg (or higher) doses are associated with reduction of IL-6 induced ex vivo pSTAT3 activation (Shi et al. 2014).

In terms of risk considerations, the proposed duration of treatment with baricitinib 4-mg in the setting of COVID-19 infection is brief (up to 14 days); to date, baricitinib has been studied and approved for long-term use in the setting of chronic autoimmune conditions. In a vaccine response study, individuals treated with baricitinib 4-mg can mount an appropriate immune response to a pneumococcal vaccine, suggesting that transient exposure to baricitinib will not result in clinically meaningful changes to adaptive immunity (Winthrop et al. 2019).

In addition, the choice of the 4-mg dose is supported by efficacy and safety data for baricitinib in Phase 2 and Phase 3 RA studies. In the RA population, there was a dose-dependent reduction in plasma IL-6 levels, assessed after 12 weeks of treatment (Stebbing et al. 2020). In ex vivo studies, there was a similar dose-dependent effect on inhibition of multiple cytokines. The baricitinib 4-mg dose is approved in multiple regions globally for the treatment of RA and is currently being studied in large ongoing global Phase 3 studies of RA, systemic lupus erythematosus, atopic dermatitis, and alopecia areata.

In summary, the potential benefit of the 4-mg dose in reducing the hyperinflammatory state caused by COVID-19 infection, and the short duration of treatment with this dose with a well-established safety profile, provides the rationale for the assessment of the benefit/risk profile of the baricitinib 4-mg dose in the setting of a randomized, controlled clinical trial in a hospital setting.

### Dose Adjustment for Renal Impairment

As detailed in the IB, baricitinib exposure increases with decreased renal function (Study I4V-MC-JADL [JADL]). Based on PK simulations, dose adjustment is not required for patients with estimated glomerular filtration rate (eGFR)  $\geq$ 60 mL/min/1.73 m^2. Patients with eGFR  $\geq$ 30 mL/min/1.73 m^2 to <60 mL/min/1.73 m^2 at screening who are randomized to the 4-mg QD dose will receive a 2-mg QD dose, to avoid exposures that exceed those of the 4-mg QD dose in patients with eGFR  $\geq$ 60 mL/min/1.73 m^2. Patients will remain on the 2-mg dose during treatment.

# 4.4. End-of-Study Definition

A participant is considered to have completed the study if he or she has completed the last scheduled procedure shown in the SoA (Section 1.3).

The "end of the study" is defined as the date of the last visit or last scheduled procedure shown in the SoA for the last participant in the study globally.

# 5. Study Population

Prospective approval of protocol deviations to recruitment and enrollment criteria, also known as protocol waivers or exemptions, is not permitted.

All screening evaluations must be conducted and reviewed to confirm that potential participants meet all eligibility criteria.

The investigator will maintain a screening log to record details of all participants screened and to confirm eligibility or record reasons for screening failure, as applicable.

Due to the criticality of participant health and the setting of this research study, verbal interview of the potential participant, or his or her legal representative or family member, may be the source for pre-existing conditions and prespecified medical history, unless otherwise specified within the eligibility criteria.

For screen failures and rescreening activities within the screening period, see Section 5.4.

# 5.1. Inclusion Criteria

Participants are eligible to be included in the study only if they meet all of the following criteria during the screening period, unless otherwise specified below:

## **Informed consent**

[1] Patient (or legally authorized representative) who gives informed consent as described in Appendix 10.1, which includes compliance with the requirements and restrictions listed in the informed consent form (ICF) and in this protocol.

## **Participant characteristics**

[2] Are male or female patients from 18 years of age (inclusive), at the time of enrollment.

Note: Contraceptive use by women should be consistent with local regulations regarding the methods of contraception for those participating in clinical studies. There are no contraceptive requirements for men. See Appendix 10.4 for contraception requirements.

## COVID-19 pulmonary infection-related inclusion criteria

- [3] Hospitalized with coronavirus (SARS-CoV-2) infection, confirmed by polymerase chain reaction (PCR) test or other commercial or public health assay in any specimen, as documented by either of the following:
  - PCR positive in sample collected <72 hours prior to randomization; OR
  - PCR positive in sample collected ≥72 hours prior to randomization (but no more than 14 days prior to randomization), documented inability to obtain a repeat sample (for example, due to lack of testing supplies, limited testing capacity, results taking >24 hours, etc.) AND progressive disease suggestive of ongoing SARS-CoV-2 infection
- [4] Require supplemental oxygen at the time of study entry and at randomization.
- [5] Have indicators of risk of progression: at least 1 inflammatory markers >ULN (CRP, D-dimer, LDH, ferritin) with at least 1 instance of elevation >ULN within 2 days before study entry.

# 5.2. Exclusion Criteria

Participants will be excluded from study enrollment if they meet any of the following criteria within the screening period, unless otherwise specified:

### Prior or concomitant therapy

[6] Are receiving cytotoxic or biologic treatments (such as TNF inhibitors, anti-interleukin-1 [IL-1], anti-IL-6 [tocilizumab or sarilumab], T-cell or B-cell targeted therapies (rituximab), interferon, or Janus kinase (JAK) inhibitors for any indication at study entry.

Note: A washout period 4 weeks (or 5 half-lives, whichever is longer) is required prior to screening, with the following exceptions:

- B-cell targeted therapies: a washout period of 24 weeks or 5 half-lives (whichever is longer)
- TNF inhibitors: a washout period of 2 weeks or 5 half-lives (whichever is longer), and
- JAK inhibitor: a washout period of 1 week or 5 half-lives (whichever is longer).

See Section 6.5.1 for requirements.

- [7] Have ever received convalescent plasma or intravenous immunoglobulin [IVIg]) for COVID-19.
- [8] Have received high dose corticosteroids at doses >20 mg per day (or prednisone equivalent) administered for ≥14 consecutive days in the month prior to study entry.

Note: Use of dexamethasone and/or other systemic corticosteroids that do not exceed the above specified dose **and** duration in the month prior to study entry is acceptable.

- [9] Strong inhibitors of OAT3 (such as probenecid) that cannot be discontinued at study entry.
- [27] Have received neutralizing antibodies, such as bamlanivimab, casirivimab and imdevimab for COVID-19.

### **Current or historical infections**

Note: Documentation from verbal interview or available medical records is acceptable.

- [10] Have diagnosis of current active tuberculosis (TB) or, if known, latent TB treated for less than 4 weeks with appropriate anti-tuberculosis therapy per local guidelines (by history only, no screening tests required).
- [11] Suspected serious, active bacterial, fungal, viral, or other infection (besides COVID-19) that in the opinion of the investigator could constitute a risk when taking investigational product. Note: Immunocompromised patients, patients with a chronic medical condition, or those taking a medication that cannot be discontinued at enrollment, who, in the judgment of the investigator, are at increased risk for serious infections or other safety concerns given the study products should be excluded.

### Vaccines

[12] Have received any live vaccine within 4 weeks before screening, or intend to receive a live vaccine during the study.

Note: Use of nonlive (inactivated) vaccinations is allowed for all participants.

### Other medical conditions or history

- [13] Require invasive mechanical ventilation, including ECMO at study entry.
- [14] Current diagnosis of active malignancy that, in the opinion of the investigator, could constitute a risk when taking investigational product.
- [15] Have a history of VTE (deep vein thrombosis [DVT] and/or pulmonary embolism [PE]) within 12 weeks prior to randomization or have a history of recurrent (>1) VTE (DVT/PE).
- [16] Anticipated discharge from the hospital, or transfer to another hospital (or another unit), which is not a study site within 72 hours after study entry.

### **Diagnostic assessments**

- [17] Have neutropenia (absolute neutrophil count <1000 cells/ $\mu$ L) (<1.00 x 10^3/ $\mu$ L or <1.00 GI/L)
- [18] Have lymphopenia (absolute lymphocyte count <200 cells/µL) (<0.20 x 10^3/µL or <0.20 GI/L)
- [19] Have alanine aminotransferase (ALT) or aspartate aminotransferase (AST) >5 times ULN
- [20] eGFR (Modification of Diet in Renal Disease [MDRD]) <30 mL/min/1.73 m^2.

Note: For each aforementioned diagnostic assessment (criteria 17, 18, 19, 20), 1 repeat testing is allowed during the screening period, and values resulting from repeat testing may be accepted for a participant's enrollment eligibility if the other eligibility criteria are met. In addition, these tests performed in the 24 hours prior to study entry will be accepted for determination of eligibility.

### Prior or concurrent clinical study experience

- [21] Have a known hypersensitivity to baricitinib or any of its excipients.
- [22] Are currently enrolled in any other clinical study involving an investigation product or any other type of medical research judged not to be scientifically or medically compatible with this study.

Note: The participant should not be enrolled (started) in another clinical trial for the treatment of COVID-19 or SARS-CoV-2 through Day 28.

### **Other exclusions**

- [23] Are pregnant, or intend to become pregnant or breastfeed during the study.
- [24] Are, in the opinion of the investigator or sponsor, unsuitable for inclusion in the study.
- [25] Are using or will use extracorporeal blood purification (EBP) device to remove proinflammatory cytokines from the blood such as a cytokine absorption or filtering device, for example, CytoSorb®.
- [26] Are, in the opinion of the investigator, unlikely to survive for at least 48 hours after screening.

## 5.3. Lifestyle Considerations

Not applicable.

## 5.4. Screen Failures

Screen failures are defined as participants who consent to participate in the clinical study but are not subsequently randomly assigned to study intervention. A minimal set of screen failure information is required to ensure transparent reporting of screen failure participants to meet the Consolidated Standards of Reporting Trials (CONSORT) publishing requirements and to respond to queries from regulatory authorities. Minimal information includes demography, screen failure details, eligibility criteria, and any serious adverse event.

## 5.4.1. Allowed Retesting of Screening Investigations

Repeating the screening labs associated with criteria [17], [18], [19], and [20] during the screening period does not constitute rescreening.

## 5.4.2. Rescreening of Individuals Who Failed Screening

Individuals who do not meet the COVID-19 pulmonary infection-related criteria and other diagnostic assessments for participation in this study (screen failures) may be rescreened.

Rescreening 1 time for any eligibility parameter that was not initially met is allowed if patient is expected to meet study requirements per investigator assessment. It is not necessary to repeat all screening requirements. Patient will not be required to reconsent due to rescreening.

Rescreened participants should be assigned a new participant number.

## 6. Study Intervention

Study intervention is defined as any investigational intervention, marketed product, placebo, or medical device intended to be administered to a study participant according to the study protocol.

## 6.1. Study Interventions Administered

#### Study interventions

This study involves baricitinib and placebo, as shown below.

Treatment Name	baricitinib	placebo
Dosage Formulation	tablet	tablet
Dosage Levels	4 mg as two 2-mg tablets*	2 placebo tablets
Routes of Administration	Oral**	Oral**
Dosing Instructions	daily	daily

\* Patients with eGFR ≥30 mL/min/1.73 m^2 to <60 mL/min/1.73 m^2 at screening who are randomized to the baricitinib 4-mg dose will receive a 2-mg QD dose, to avoid exposures that exceed those of the 4-mg QD dose in patients with eGFR ≥60 mL/min/1.73 m^2. Patients on the baricitinib 2-mg QD dose will receive a single 2-mg tablet and will remain on this dose during the study if eGFR ≥30 mL/min/1.73 m^2 to <60 mL/min/1.73 m^2 at screening. Patients will remain on 2-mg dose during treatment.

Patients with eGFR  $<60 \text{ mL/min}/1.73 \text{ m}^2$  at screening who are randomized to placebo will receive one placebo tablet.

\*\* Baricitinib will be administered as a 4-mg dose orally (po) (two 2-mg tablets) or crushed for NG tube, given daily, for the duration of the hospitalization up to a 14-day total course. A placebo will be given as 2 tablets po or crushed for NG tube, daily, for the duration of the hospitalization up to a 14-day total course.

Investigational product will be administered to the patient at the study site. No investigational product will be provided to patients once discharged from the hospital.

## Packaging and labeling

Study interventions (baricitinib and placebo) will be supplied by the sponsor or its designee in accordance with current Good Manufacturing Practice (cGMP). Clinical trial materials will be labeled according to the country's regulatory requirements. All IPs will be stored, inventoried, reconciled, and destroyed according to applicable regulations.

## 6.2. Preparation/Handling/Storage/Accountability

The Pharmacy Manual provides instructions for the preparation, handling, and storage of baricitinib drug product and placebo, and describes site responsibility and accountability for the administered products.

Investigators should consult the information provided in the Pharmacy Manual or the label for specific administration information, including warnings, precautions, contraindications, adverse reactions, and dose modifications.

## Handling and storage

Follow the storage and handling instructions on the IP packaging.

## Site responsibilities and accountability

The following are responsibilities of the investigator or his or her designee:

- The investigator or designee must confirm appropriate temperature conditions have been maintained during transit for all study intervention received and that any discrepancies are reported and resolved before use of the study intervention.
- Only participants enrolled in the study may receive study intervention, and only authorized site staff may supply or administer study intervention. All study intervention must be stored in a secure, environmentally controlled, and monitored (manual or automated) area in accordance with the labeled storage conditions with access limited to the investigator and authorized site staff.
- The investigator, institution, or the head of the medical institution (where applicable) is responsible for study intervention accountability, reconciliation, and record maintenance (that is, receipt, reconciliation, and final disposition records).

Further guidance and information for the final disposition of unused study interventions are provided in the Pharmacy Manual.

The investigator or designee is also responsible for

- explaining the correct use of the study interventions
- verifying that instructions are followed properly
- maintaining accurate records of IP dispensing and collection, and
- returning all unused medication to Lilly or its designee at the end of the study.

Note: In some cases, sites may destroy the material if, during the investigative site selection, the evaluator has verified and documented that the site has appropriate facilities and written procedures to dispose of clinical materials.

# 6.3. Measures to Minimize Bias: Randomization and Blinding

Blinding will be maintained in the Phase 3 study.

Method of treatment assignment

Patients who meet all criteria for enrollment will be randomized in a 1:1 ratio (baricitinib 4-mg: placebo) at Day 1.

Randomization will be stratified by these factors:

- disease severity:
  - $\circ$  hospitalized not requiring supplemental oxygen, requiring ongoing medical care

- hospitalized requiring supplemental oxygen by prongs or mask
- $\circ~$  hospitalized requiring non-invasive ventilation or high-flow oxygen
- age (<65 years;  $\geq$ 65 years)
- region (United States, Europe, rest of world), and
- dexamethasone and/or other systemic corticosteroid used at baseline for primary study condition (Yes/No).

Assignment to treatment groups will be determined by a computer-generated random sequence using an interactive web-response system (IWRS).

## Emergency unblinding

Emergency unblinding for adverse events may be performed through the IWRS. This option may be used ONLY if the participant's well-being requires knowledge of the participant's treatment assignment. All actions resulting in an unblinding event are recorded and reported by the IWRS.

If a participant's study treatment assignment is unblinded to the investigator, to site personnel performing assessments, or to the participant, the participant must be discontinued from the study, unless the investigator obtains specific approval from the sponsor's medical monitor for the participant to continue in the study (Section 7.1.1).

In case of an emergency, the investigator has the sole responsibility for determining if unblinding of a participants' intervention assignment is warranted. Participant safety must always be the first consideration in making such a determination. Where feasible and when timing of the emergent situation permits, the investigator should attempt to contact the Lilly medical monitor before unblinding a participant's treatment assignment.

In cases where there are ethical reasons to have the participant remain in the study, the investigator must obtain specific approval from the sponsor for the participant to continue in the study.

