A follow-up visit approximately 28 days after last dose is required for all randomized patients, including those discharged from hospital before Day 14. Another follow-up visit occurs at approximately Study Day 60. These follow-up visits can be conducted as telephone visits.

Discharge from the hospital prior to Day 14 is not considered early discontinuation from the study drug or from the study. All randomized patients, including patients meeting criteria for early discontinuation of study drug, as specified in Section 7.1, should be encouraged to remain in the study for the scheduled study assessments specified in the Schedule of Activities (SoA) (Section 1.3). Patients who prematurely discontinue from the study should have an ETV and follow-up visits, if possible, as shown in the SoA.

The study schema is presented in Section 1.2.

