#### 7.1.1. Criteria for Permanent Discontinuation of Study Drug

Data collection and safety follow-up when study drug is permanently discontinued

If a patient permanently discontinues study drug early (that is, prior to hospital discharge or Day 14, whichever comes first), the patient should remain in the study and have the scheduled study assessments specified in the SoA (Section 1.3). Every effort should be made to encourage participants to remain in the study for the duration of their planned outcome assessments. Participants should be educated on the continued scientific importance of their data, even if they discontinue study drug.

Unless the participant withdraws consent or meets other criteria listed in Section 7.2, those who discontinue study drug early will remain in the study. The reason for participant discontinuation of study drug should be documented in the CRF.

If a patient who is not receiving study drug is unwilling or unable to continue the scheduled study assessments, the site personnel should attempt to collect as much follow-up information as possible, including, at minimum, information specified for an early termination visit (ETV) **and** information for the follow-up visits, including the Study Day 60 visit.

Criteria for permanent discontinuation of study drug

Possible reasons leading to permanent discontinuation of study drug include, but are not limited to, the following:

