#### Other reasons

• Unblinding: If an investigator, site personnel performing assessments, or participant is unblinded, the participant must be discontinued from the study drug and continue to post-treatment follow-up. In cases where there are ethical reasons to have the participant continue on study drug, the investigator must obtain specific approval from the sponsor or designee for the participant to continue.

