# 7.2. Participant Discontinuation/Withdrawal from the Study

Participant discontinuation (withdrawal from the study) is expected to be uncommon.

A participant may withdraw from the study in the following circumstances:

- at any time at his or her own request, or at the request of his or her designee (for example, parents or legal guardian)
- at the discretion of the investigator for safety, behavioral, compliance, or administrative reasons
- if the participant enrolls in any other clinical study involving an investigational medicinal product or enrollment in any other type of medical research judged not to be scientifically or medically compatible with this study
- if the participant, for any reason, needs to be transferred to another hospital or another hospital unit
- if the participant, for any reason, requires treatment with another therapeutic agent that has been demonstrated to be effective for treatment of the study indication. In this case, discontinuation from the study occurs prior to introduction of the new agent.

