## Data collection and follow-up for participants who discontinue the study

At the time of discontinuing from the study, an ETV and final follow-up visits should be conducted, if possible, as shown in the SoA. See the SoA for data to be collected at the time of study discontinuation and follow-up and for any further evaluations that need to be completed. The participant will be permanently discontinued both from the study intervention and from the study.

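### Protocol Section 6.3 takes an unblinded participant out of the study by default, while Section 7.1.1, which it cites, stops study drug only and keeps follow-up going

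*Protocol*

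**What the plan says.** Protocol Section 6.3 (Emergency unblinding) covers unblinding of the investigator, of site staff who perform assessments, or of the participant. Its rule is that "the participant must be discontinued from the study, unless the investigator obtains specific approval" of the medical monitor for staying in the study, and it points to Section 7.1.1. Its closing paragraph repeats the idea: "In cases where there are ethical reasons to have the participant remain in the study, the investigator must obtain specific approval".

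Protocol Section 7.1.1 (Other reasons) covers the same three parties. There, "the participant must be discontinued from the study drug and continue to post-treatment follow-up". The exception is also different: "In cases where there are ethical reasons to have the participant continue on study drug, the investigator must obtain specific approval".

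Three other parts of the protocol bear on the point:

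- Section 7.1.1, on data collection: apart from withdrawal of consent or a Section 7.2 criterion, "those who discontinue study drug early will remain in the study".
- Section 4.1: all randomized patients, including those who meet drug-stopping criteria, "should be encouraged to remain in the study for the scheduled study assessments".
- Section 7.2 opens its list with "A participant may withdraw from the study in the following circumstances". None of the five circumstances that follow names unblinding. For anyone who does leave the study, "The participant will be permanently discontinued both from the study intervention and from the study", and the early termination and final follow-up visits are held only where feasible.

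**The concern.** The two sections give different mandatory defaults for one event and attach the approval to different things: staying in the study, or staying on drug. The sentence in Section 6.3 refers the reader to a section that states another rule.

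Post-unblinding outcome data are at stake. The primary endpoint runs to Day 28 and is built from daily clinical status (Protocol Section 8.1.1). A participant who leaves the study on unblinding, without a primary event so far, may contribute no status from that day to Day 28. Emergency unblinding is for adverse events, so these patients are not a random sample. The SAP (Section 6.4.3) adopts a treatment policy strategy, under which status after the event is exactly what is wanted.

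Safety surveillance is affected too. Under Protocol Section 8.3.1, investigators need not actively look for adverse events once a participant has discontinued the study. Section 6.3 would by default end active surveillance in patients unblinded because of an adverse event, although Section 8.3.3 still has reported serious events followed up.

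**Working it through.** **Text comparison.**

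| | Section 6.3 | Section 7.1.1 (Other reasons) |
|---|---|---|
| Trigger | Investigator, assessing staff or participant unblinded | Same |
| Default | Leave the study | Stop drug, continue to follow-up |
| Approval is for | Remaining in the study | Remaining on drug |

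The following all agree with the right-hand column:

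- the general rule in Section 7.1.1 for patients who stop drug early;
- Section 4.1;
- the intention-to-treat definition in Appendix 5, which calls for follow-up whatever the compliance with treatment;
- the treatment policy strategy in SAP Section 6.4.3.

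Nothing in either document gives a reason to end outcome collection after unblinding. Section 6.3 states its rule twice, so it is not a single slip.

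**What happens to the data.** SAP Table KHAA.6.4 counts the primary endpoint as missing only when it cannot be established from the remaining data, so events before unblinding still count. What stays missing is imputed with the Markov model of SAP Appendix 2. That model is fitted separately by arm and by strata of baseline ordinal score and steroid use, and it assumes missing at random. It uses the ordinal states and, where known, that the patient is alive. It does not use the adverse event. If that event carries risk beyond the observed state, the imputed risk is too low.

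**Bound per lost patient.** The documents have no figure to reproduce here, so this is a new calculation. A true outcome is 0 or 1 and its imputed probability lies between 0 and 1. One lost outcome can therefore move the crude treatment difference by at most 1 divided by the number in the arm.

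- Population 1 at 1400 patients: 1400/2 = 700 per arm; 1/700 = 0.143 percentage points.
- Population 1 at the 1700 cap (SAP Section 6.16.2): 1700/2 = 850 per arm; 1/850 = 0.118 points.
- Population 2 at the illustrative 40% not on steroids (the sample size sections assume 60% on them): 0.40 × 1400 = 560; 280 per arm; 1/280 = 0.357 points. The SAP revision history reports Population 2 as much smaller than anticipated, so the true bound there is larger.

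**Shift in Population 1 under an assumed gap.** Let g be true risk minus imputed risk. The documents do not give g; the range below is assumed. The shift per net lost patient is g/700, and the net imbalance needed for 0.5 points is 0.005 × 700/g = 3.5/g.

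| g | Shift per net patient (points) | Net imbalance for 0.5 points |
|---|---|---|
| 0.10 | 0.014 | 35 |
| 0.25 | 0.036 | 14 |
| 0.50 | 0.071 | 7 |

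The 0.5-point mark is a chosen yardstick, about 7% of the 7.5-point effect in the first power scenario (0.5/7.5). Losses equal in number and gap in the two arms cancel in the difference.

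**The case against.** The best reply is that this is a wording slip with its own remedy: Section 6.3 cites Section 7.1.1, so a careful site will find the more specific rule. Loss is also not automatic:

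- The medical monitor can approve staying in.
- Section 4.1 and the Schedule of Activities require the follow-up contacts for all randomized patients.
- The early termination visit includes a clinical status assessment.
- Section 8.1.1 has the hospitalization part of clinical status completed daily even without patient contact.
- The imputation can use the knowledge that a patient is alive.

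Section 7.2 also lets the investigator withdraw a participant at discretion. Unblinding is restricted to cases where the patient's welfare depends on it, so numbers should be low.

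Most of this stands as a limit on size. It does not remove the conflict. A cross-reference does not cancel a mandatory sentence that says something else. The discretion in Section 7.2 is permissive and does not amount to a rule that unblinded patients must leave. The documents do not say whether the hospitalization item continues after study discontinuation.

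Two practical points are right. Section 7.1.1 speaks of post-treatment follow-up, which read literally does not by itself secure daily status to Day 28; the general rule earlier in that section does. And because Section 10.1.1 requires ethics approval before a protocol change takes effect, a letter to sites would not be enough.

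**Conclusion.** The concern holds. Section 6.3 is wrong as written: it contradicts the section it cites, and it departs from the protocol's general rule on follow-up and from the estimand. A site that obeys it can lose Day 28 outcomes and active safety follow-up in patients unblinded for adverse events.

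The numerical effect is probably small and cannot be totalled without an unblinding rate. Each lost outcome is worth at most 0.14 points in Population 1 and 0.36 points in the illustrative Population 2. A bias of 0.5 points in Population 1 would need a net imbalance of 7 to 35 lost patients, on the assumed risk gap of 0.50 to 0.10. The case for correction rests on the contradiction and the small amount of text to change. It does not depend on a large expected bias.

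**What to change.** In Section 6.3, replace the rule so that an unblinded participant stops study drug and continues all scheduled assessments, including daily clinical status through Day 28 and the Day 60 contact. Sponsor approval should be needed only for continued dosing, as in Section 7.1.1. In the closing paragraph of Section 6.3, change both references to staying in the study so that they refer to staying on study drug.

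It would be tidy, though not essential, to have the unblinding item in Section 7.1.1 refer to the scheduled assessments as well as to post-treatment follow-up. If there is concern that an unblinded assessor may be biased, later assessments can be flagged; outcomes such as death or intubation should still be collected.

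The cost is two reworded sentences in a protocol amendment, with ethics approval across the 12 countries listed in the SAP, so it is best combined with another amendment. No visits are added, and the sponsor keeps control over continued dosing.
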